7.2 SAFETY ENDPOINTS

- Change from baseline to each scheduled assessment in BMD measured by DXA of lumbar spine (L1-L4), femoral neck, and total hip
- Incidence and severity of treatment emergent adverse events (TEAEs)
- Incidence and severity of hypoestrogenic TEAEs (hot flush)
- Time to the first post-treatment menses
- Changes in clinical laboratory assessments (hematology, biochemistry, coagulation parameters, hormones, lipids and urinalysis) from baseline to each scheduled assessment
- Any pathological changes from baseline in the endometrium as assessed by histology from endometrial biopsies

- Changes from baseline to each scheduled assessment in any other safety parameter including weight, vital signs, ECG, gynecological assessments and endometrial thickness

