At any time during the study, in case of endometrial biopsy diagnosis being hyperplasia of any type (with or without atypia) or worse (neoplasm) for patients on treatment, the laboratory will send an alert to the site and the Sponsor. The medical monitor will contact the sites to discuss the proceeding in line with local practice. The subject will be discontinued from the treatment, (and will not be eligible to enter the extension study), will enter the follow-up period (unless she is discontinued prior to Month 3 visit) and will be advised to consult for a gynecological evaluation and treatment.

Biopsy should be recommended (for cause) for subjects with heavy/suspicious bleeding. Results from these procedures should be documented in the eCRF.

Endometrial biopsy samples will be performed with the Pipelle de Cornier® (or equivalent), as described in the manual provided by the central laboratory.

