10.7.2 Subject Withdrawal

Subjects will be informed that they have the right to withdraw from the study at any time, without prejudice to their medical care, and that they are not obliged to state the reason(s). Any withdrawal must be fully documented in the eCRF exit form.

The Investigator may withdraw a subject at any time if this is considered to be in the subject's best interest.

In addition, the sponsor could make a decision to temporarily or permanently discontinue the study for safety, ethical, compliance or other reasons. In this case, the subject's participation may be ended prematurely without asking for her consent.

In case of early discontinuation, the subject will be instructed to complete the relevant eDiary questionnaires as soon as possible upon treatment discontinuation.

Subjects who did not receive the study drug will be withdrawn from the study and no further study procedures will be performed.

Withdrawal during treatment period:

Subjects who discontinue between Day 1 and Month 3 should undergo the procedures required at Month 6 (except the DXA scan and the endometrial biopsy if a biopsy was obtained at screening) and will not enter the 6-month follow-up period.

Subjects discontinuing the study treatment between Month 3 and Month 6 should undergo the procedures required at Month 6. These subjects will enter a 6-month follow-up period and will continue daily eDiary recording for 6 months and up to Month 6 FU visit in order to continue to collect efficacy data.

PK sampling is not required if the subject had no IMP administration the day prior to the withdrawal visit.

Withdrawal during follow-up period:

Subjects discontinuing participation in the study during the follow-up period should undergo the procedures required at Month 6 FU visit, which includes completion of all ClinRO and ePRO questionnaires, except the DXA in case of discontinuation before Month 3 FU visit.

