For other safety data, data from early discontinuation should be compared to theoretical visits dates. Only assessments within the window of theoretical date +/-14 days will be used for analyses, if it is planned to have a such assessment at this visit and no other assessment is in the window. If a subject discontinued in the main treatment period, date will be compared to the theoretical visit dates in main treatment period as described in Table 3. If a subject discontinued in the follow-up period, date will be compared to the theoretical visit dates in Follow-up period from Table 4. For unscheduled safety assessments, if the unscheduled assessment occurs in a window of +/-14 days of a planned eCRF visit for

Sponsor:	ObsEva			
Protocol:	18-OBE2109-00	18-OBE2109-003		
Document Version No.:	V5.0	Document Date:	13-JUN-2022	

which it was planned per protocol to have such assessment, and no assessment was done for that visit, the unscheduled assessment will be assigned to that visit. If an unscheduled assessment is equally distant from two eCRF visits with no corresponding safety assessment, the unscheduled assessment will be assigned to the next visit.

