4.8.8. Transvaginal Ultrasound (TVUS)

TVUS will be performed at Screening, Month 3, Month 6, Month 3 and Month 6 of the Follow-up period.

Actual values and changes from baseline will be summarized by treatment group and overall for uterus length, width, and depth in mm and corresponding uterine volume in cm3, as well as endometrium thickness in mm.

The number and percentage of subjects with any ovarian endometrioma with a diameter of 7 cm or greater, and presence of any uterus, left ovary or right ovary abnormality over time will be presented by treatment group and overall.

Sponsor:	ObsEva		
Protocol:	18-OBE2109-003		
Document Version No.:	V5.0	Document Date:	13-JUN-2022

4.8.9. **Other Examinations**

At least two endometrial biopsies for histological assessment were obtained for each subject:

- One at screening, unless an endometrium biopsy was performed within the past 6 months of the screening visit, which shows no atypical hyperplasia or adenocarcinoma and for which slides are available for current study assessment through retrospective central laboratory reading.
- One at Month 6 if the endometrium thickness via TVUS is > 5 mm
- One at Month 1 FU, 2 FU, 3 FU, 4 FU, 5 FU or 6 FU if not obtained at Month 6 or if the preceding biopsy diagnosis is different than "benign endometrium"

A summary at each time point will be performed (number and percentage of subjects with normal, abnormal, not assessable).

Biopsy diagnosis will be summarized by classification and primary diagnosis at each visit. Subjects will be counted only once per classification and diagnosis. A subject can be counted in several diagnoses.

Possible classifications and diagnoses are:

- Benign Endometrium without Hyperplasia or Atypia: Proliferative, Atrophic, Metaplastic Changes, Secretory, Indeterminate, Inactive, Polyp, Endometritis, Menstrual phase, Other
- Hyperplasia: Simple with Atypia, Simple without Atypia, Complex with Atypia, Complex without Atypia
- Malignant Endometrial Neoplasm: Carcinoma, Sarcoma, Other Malignant, Not applicable.

If any diagnosis does not correspond to any on the list, the diagnosis will be coded as: Other Malignant if classification is Malignant Endometrial Neoplasm, and Other for any other classification.

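### Exit biopsies before Day 155 and most for-cause biopsies before Month 6 have no row in the by-visit histology tables; a worst post-baseline diagnosis table would count them

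*SAP*

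**What the plan says.** **Endpoint.** Protocol 7.2 lists as a safety endpoint "Any pathological changes from baseline in the endometrium as assessed by histology from endometrial biopsies". It names no visit.

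**When biopsies are taken.** Protocol Appendix A and SAP Table 1 plan biopsies at screening and Month 6 only. The Month 6 biopsy is done when the endometrium exceeds 5 mm on ultrasound. Two other routes exist during treatment:
- Protocol 10.7.2: "Subjects discontinuing the study treatment between Month 3 and Month 6 should undergo the procedures required at Month 6". This brings in the biopsy, subject to the same 5 mm condition.
- Protocol 10.4.5: "Biopsy should be recommended (for cause) for subjects with heavy/suspicious bleeding". No time limit is set.

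Protocol 10.4.5 and 10.7.2.1 stop treatment when a biopsy shows hyperplasia of any type or worse.

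**How dates map to visits (SAP 4.2.9).** By default the visit recorded in the eCRF is used. Under Other Safety Data there are two special rules:
- Early discontinuation: "Only assessments within the window of theoretical date +/-14 days will be used for analyses, if it is planned to have a such assessment" at the visit, and only if no other assessment is in the window. For a woman who stops in the treatment period, the "date will be compared to the theoretical visit dates in main treatment period as described in Table 3".
- Unscheduled: the assessment goes to a visit if it lies within 14 days of a planned eCRF visit for "which it was planned per protocol to have such assessment, and no assessment was done for that visit".

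**How biopsies are reported (SAP 4.8.9).** Results are summarized at each time point, and "Biopsy diagnosis will be summarized by classification and primary diagnosis at each visit". All results are also listed. No table covers any time after baseline, and none gives a worst diagnosis per subject.

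**The concern.** The endpoint asks whether any pathological change occurred, but the tables show only what can be placed in a visit row. Two kinds of on-treatment biopsy that the protocol itself foresees are poorly placed for that: exit biopsies from women who stop between Months 3 and 6, and for-cause biopsies taken for abnormal bleeding.

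The for-cause biopsies matter most. No biopsy is scheduled between first dose and Month 6, so a hyperplasia diagnosis that stops treatment in that period will in practice come from an unscheduled sample, which is the kind least likely to get a row. Whether a biopsy is tabulated would then depend partly on what prompted it, and the histology count in an arm could be too low.

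The SAP does not treat other safety data this way. Liver tests get a shift table to the worst on-treatment value that takes in unscheduled results (SAP 4.8.4). The suicidality scale is summarized at any time after baseline (SAP 4.8.10). The Month 6 DXA window is 28 days on each side (SAP 4.2.9).

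**Working it through.** **1. The plan's own date.** SAP 4.2.11 sets Month X = Day 1 + 28 × X. For Month 6 this is 1 + 168 = Day 169, which agrees with SAP Table 3.

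**2. Window for an early-discontinuation biopsy.** Month 6 is the only Table 3 visit with a planned biopsy, so the window is 169 − 14 = Day 155 to 169 + 14 = Day 183.

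**3. Exit biopsies, Month 3 to Month 6.** Month 3 is 1 + 84 = Day 85, so possible stopping days run from Day 85 to Day 168.
- All days: 168 − 85 + 1 = 84
- Inside the window: Days 155 to 168 = 14
- Outside: 84 − 14 = 70, and 70/84 = 83%

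This assumes the biopsy is done on the day treatment stops. If it comes 7 days later (an assumed delay), stopping Days 85 to 147 are outside: 63/84 = 75%.

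**4. For-cause biopsies on treatment.** Take Days 1 to 168 with the Month 6 visit on Day 169.
- Within 14 days of Month 6: Days 155 to 168 = 14
- Outside: 168 − 14 = 154, and 154/168 = 92%

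The remaining 14 days qualify only if no biopsy was done at the Month 6 visit.

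**5. Could another row catch them?**
- Screening: no. SAP 4.2.9 limits that row to biopsies before the first dose.
- Month 1 follow-up: no. For an early discontinuer, the earliest in-window visit is 28 − 7 = 21 days after the last intake (Protocol 10.2.3.1). The unscheduled-data window then opens 21 − 14 = 7 days after stopping, too late for an on-treatment sample.

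**6. The rules applied to illustrative records.**

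| Biopsy | Rule that applies | Row in the histology tables |
|---|---|---|
| Scheduled Month 6, Day 171 | eCRF visit label | Month 6 |
| Exit, Day 130 | outside Days 155 to 183 | none |
| Exit, Day 160, no other in window | inside the window | Month 6 |
| For-cause, Day 110 | no planned biopsy visit within 14 days | none |
| For-cause, Day 160, Month 6 biopsy also done | visit already has an assessment | none for the for-cause sample |

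**The case against.** Much of the case on the other side stands.

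- **Scheduled biopsies are safe.** A reader might infer that every treatment-period biopsy more than 14 days from Month 6 is discarded. The documents do not say so: scheduled biopsies keep their eCRF visit. The exclusion is stated only for early-discontinuation data. The unscheduled rule assigns visits and excludes nothing in words; for-cause biopsies are left out because every table is by visit.
- **The diagnosis need not vanish from the report.** Under Protocol 12.1.2 a clinically significant finding that leads to discontinuation of study drug is reportable as an adverse event. SAP 4.8.2 tabulates treatment-emergent events by arm from first dose to 30 days after stopping, with no visit window, and all biopsies are listed. It would be wrong to say that such results survive only in a listing. But an adverse event term is not a histology classification, and its denominator is all treated women rather than those biopsied.
- **Exit biopsies are not selected for pathology.** Women stop for many reasons (Protocol 10.7.2.1), and the exit biopsy depends on the 5 mm condition. The link from hyperplasia to stopping to omission fits only for-cause biopsies.
- **Follow-up may add a later sample.** Women stopping between Months 3 and 6 enter follow-up. Protocol 10.2.3, Appendix B and SAP 4.8.9 call for repeat biopsy after a non-benign result; Protocol 10.4.5 excepts hyperplasia and malignancy. These passages must be reconciled. On either reading, a sample taken off drug does not report the on-treatment diagnosis, and women who stop before Month 3 do not enter follow-up.
- **A non-assessable Month 6 sample.** One might suppose that it displaces a readable unscheduled one. The SAP does not say whether such a sample counts as an assessment done.

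**Conclusion.** The point holds as a gap in the histology tables. Exit biopsies taken before Day 155 and most for-cause biopsies taken before Month 6 have no row, although the endpoint covers any pathological change. The share is 83% of the calendar days on which a Month 3 to Month 6 discontinuer can stop (biopsy on the stopping day), and 92% of on-treatment days for a for-cause biopsy (Month 6 visit on Day 169). These are shares of days, not of women or biopsies; the documents give no counts.

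The by-arm count can therefore be too low, by an amount that cannot be estimated from the documents. A reader might go further and infer a biased comparison against placebo because one active arm contains estradiol. That is not shown: the rule is the same in every arm, and that arm also contains norethisterone acetate. Nor do the documents give a hyperplasia rate from which to judge how much a single omitted case would matter.

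This is a reporting weakness that should be corrected. It does not mean that the safety data are lost.

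**What to change.** Leave the by-visit table and the SAP 4.2.9 window rule as they are. Add to SAP 4.8.9 one table of worst post-baseline diagnosis per subject, by arm:

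- **Biopsies used:** all main-study biopsies after first dose (scheduled, early-discontinuation, for-cause, other unscheduled, follow-up), taken before any extension dose and regardless of the 4.2.9 window.
- **Denominator:** women with at least one assessable post-baseline biopsy.
- **Severity order:** SAP 4.8.9 already ranks hyperplasia and malignant diagnoses for discordant readings. Use that order, with benign below it.
- **Layout:** on-treatment and off-treatment samples shown separately, with time on drug.

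The cost is a short SAP addition and one descriptive table. No hypothesis test is involved, so alpha is not affected. The drawback is that biopsies taken at different exposure times are pooled, which is why time on drug should be displayed.

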4.2.10. Baseline Definition

The primary endpoint and other efficacy endpoints based on daily e-diary data (DYS, NMPP, dyschezia, overall pelvic pain, dyspareunia, analgesic use, difficulty in daily activities, uterine bleeding, missing school or work, having to sleep or laying down) will base the baseline calculation on diary data from menstrual cycles of the screening period. The screening period must cover at least two full menstrual cycles. The following rules apply to select the two baseline menstrual cycles for assessment of eligibility and baseline:

- If only two full screening cycles are covered prior to Day 1: those two screening cycles should be used for both eligibility assessment and baseline calculation.
- If 3 full screening cycles are covered during the screening period, for logistical reason, as allowed per protocol: "If for logistical reasons beyond her control, the subject is unable to come to the clinic for Day 1 within the acceptable time window (1st to 7th day inclusive of the cycle) then the subject will be allowed to start Day 1 in the following cycle (again on the 1st to 7th day of the cycle). In this case, the eligibility assessments should be assessed based on the first two cycles only"; the two first screening cycles should be used for both eligibility assessment and baseline calculation
- If more than 3 full screening cycles are covered during the screening period: the last two menstrual cycles prior to the baseline visit will be considered for both eligibility assessment and baseline calculation.
- Due to possible technical issues with the e-diary device, some data during screening menstrual cycle may not have been collected properly. Consequently the menstrual cycles may not be considered as valid for assessment of eligibility and baseline and cycles other than the first and/or second ones might be used.

ObsEva will provide an excel file listing all the menstrual cycles that were used for measurement of eligibility and baseline values.

Further details on baseline calculations are specified in the analysis sections for each endpoint.

The baseline DXA assessment will be derived as the latest non-missing DXA assessment with acceptable quality (accepted="Yes") prior to the baseline visit or the first non-missing assessment with acceptable quality (accepted="Yes") done up to 10 days after the baseline visit if there is no assessment prior to baseline.

CRS-BS-TP-000005 V 1.0

Sponsor:	ObsEva		
Protocol:	18-OBE2109-003		
Document Version No.:	V5.0	Document Date:	13-JUN-2022

For other data, unless otherwise specified, baseline will be defined as the data most recently collected prior to the first dose of IMP.

4.2.11. Last treatment administration date, End of Study date and Period definitions

The last treatment administration date will be defined as the date from the treatment termination of main period eCRF page. If this date is missing, the last date with a drug intake in eDiary strictly inferior to Month 6 date or the last date with a drug intake in eDiary available if the subject discontinued will be used.

For each 28-day period prior to Month X (except Month 6), the end of the period will be defined as the Month X visit date. If subject discontinued prior to Month X, the end of the period will be the date from the treatment termination of main period eCRF page or the last date with a drug intake in the eDiary if missing. If the subject missed the Month X visit (but did not discontinued), the subject might still have filled the diary during that time: the theoretical Month X date will be used to define the end of the 28-day period. The theoretical Month X is defined with respect to Day 1 as Month X= Day 1+ 28*X. Theoretical visits are presented in Table 3 of Section 4.2.9.

For the 28-day period prior to Month 6, the end of the period will be defined as the last treatment administration date.

The end of study date will be Month 6 date -1 day for subjects entering the Extension, and the last assessment date defined as last eCRF (excluding AE and CM end dates) or eDiary date in main study or main Follow-up for subjects not entering the Extension. This will not necessarily be the same date as last assessment date as recorded in the eCRF.

Note: For summaries by visit (efficacy or safety), the Month 6 assessments will be included in the main study analyses. For Adverse Events, Concomitant Medications and Daily diaries, data collected on Month 6 date will be part of the extension for subjects entering the extension study, and be part of the Follow-up period for subjects entering the main study follow-up period.

The main treatment period will be defined as Day 1 up to (Month 6 date -1) or treatment discontinuation date.

The main follow-up period will be defined as the Month 6 date or (treatment discontinuation date+1) up to the end of study date (for subjects who entered the follow-up).

4.3. Interim Analyses

An interim analysis is not planned for this study. This SAP will however be updated twice prior to unblinding and analysis of the data up to Month 6, in order to incorporate the results of the blinded meaningful change estimation analyses at Month 3 and at Month 6.

Sponsor:	ObsEva		
Protocol:	18-OBE2109-00	3	
Document Version No.:	V5.0	Document Date:	13-JUN-2022

At Month 6 Database Lock, the blinded meaningful change estimation for ranked secondary endpoints based on Month 6 data will be performed by a blinded team at Cytel and a blinded team at Clinical Outcome Solutions, while a Cytel restricted team will be unblinded to produce on the Month 6 CSR analysis. The blinded and unblinded teams will not be in contact, and any unblinded results will be provided to Sponsor only after the Month 6 meaningful change estimation has been completed and the SAP updated.

Results will be presented twice: after Month 6 completion and after Month 6 Follow-up completion.

4.4. Subject Disposition

A tabulation of subject disposition will be presented, including the number of subjects screened, randomized, who received at least one dose of study drug, the number in each subject population for analysis, the number of subjects who withdrew prior to completing the study, and reasons for withdrawal, by treatment group and overall, for randomized subjects and for safety population.

A subject will be considered to have completed study if the subject completed the treatment and followup periods, or completed the treatment period and entered the extension study.

The number of subjects who completed each visit will be summarized by treatment group and overall, for the FAS population.

The following listings will be presented:

- Study completion information, including the reason for premature study withdrawal, if applicable;
- Inclusion/exclusion criteria not met for Screened Subjects;
- Subject inclusion in each of the analysis sets (Randomized Set, Full Analysis Set, Per Protocol set, Threshold Analysis Set, M6 Threshold Analysis Set, PK Analysis Set, Safety Analysis Set, Follow-up Set, and Follow-up Safety Set).

4.5. Demographic and Baseline Characteristics

Baseline, demographic and medical history information will be analyzed for the (SAF), FAS and PP set. No formal statistical comparisons will be performed.

4.5.1. **Demographics**

Demographics and baseline characteristics will be summarized by treatment group and overall using descriptive statistics.

Sponsor:	ObsEva		
Protocol:	18-OBE2109-003		
Document Version No.:	V5.0	Document Date:	13-JUN-2022

Demographics and baseline data include Age (years), Gender, Ethnicity, Race, Height (cm), Weight (kg), Body Mass Index (kg/m2), Systolic Blood Pressure (mmHg), Diastolic Blood Pressure (mmHg), Heart Rate (beats/minute), QTc interval (Fridericia) (ms).

BMI is auto-calculated, defined as: Weight (kg)/(Height*Height) (m²).

Demographic and Baseline data will be provided in data listings.

4.5.2. Baseline Disease Characteristics

The definition of the two baseline menstrual cycles is described in section 4.2.10

Baseline Dysmenorrhea (DYS) and Non-Menstrual Pelvic Pain (NMPP) will be calculated by averaging over the two baseline menstrual cycles, the e-diary daily answers of Endometriosis Related Pelvic Pain (PP VRS Questionnaire). Responses of "None," "Mild," "Moderate," and "Severe" will be assigned a score of 0, 1, 2, and 3, respectively. Dysmenorrhea will be computed using days with uterine bleeding, defined as those days on which the subject records any uterine bleeding or spotting in the subject eDiary; Non-Menstrual Pelvic Pain will use days with no uterine bleeding.

The baseline analgesic use will be calculated as the mean of daily pill count of analgesics over the two baseline menstrual cycles for each class of rescue analgesics (endometriosis-associated: Ibuprofen, Narcotic Analgesic) collected in the eDiary, separately for bleeding days, non-bleeding days and overall.

Dysmenorrhea, Non-Menstrual Pelvic Pain and Analgesic use will be summarized as continuous variables

The average duration of the two baseline menstrual cycles (days) will be summarized. The duration (days) of each of the two individual eligible baseline menstrual cycle will be calculated using the (menstrual start dates provided in the excel file. The duration is computed as (start date of $Cycle_{x+1}$ – start date of $cycle_x$).

The average number of days with uterine bleeding over the two baseline menstrual cycles will be summarized as continuous variables.

The number and percentage of subjects with Normal, Abnormal, Abnormal clinically significant (or Not Assessable) results for Physical Examination, Gynecological Examination, Breast Examination, Mammography, Endometrial Biopsy and PAP Smear assessments will be presented by treatment group and overall. Abnormality details will be provided in data listings.

Transvaginal ultrasound data (i.e., presence of ovarian endometrioma with a diameter of 7 cm or greater, uterus length, width, and depth in mm and corresponding calculated uterine volume in cm3 (using the prolate ellipsoid formula [L x H x W x 0.523]), endometrium thickness in mm, and presence of any uterus, left ovary or right ovary abnormality) will be summarized.

Dysmenorrhea, Deep Dyspareunia, Non Menstrual Pelvic Pain, Total Pelvic Pain (None: 0, Mild: 1-3, Moderate: 4-6, Severe: 7-9), Pelvic Tenderness, Induration, Total Physical Sign Score (None: 0, Mild: 1-2, Moderate: 3-4, Severe: 5-6) and Composite Pelvic pain and Physical Sign Score (None: 0, Mild: 1-2, Moderate: 3-5, Severe: 6-10, Very Severe 11-15) from the Modified Biberoglu & Behrman symptom

Sponsor:	ObsEva			
Protocol:	18-OBE2109-00	18-OBE2109-003		
Document Version No.:	V5.0	Document Date:	13-JUN-2022	

severity scale assessment as collected in eCRF will be summarized at baseline as categorical variables with the following categories: None, Mild, Moderate, Severe (Very Severe).

Baseline Disease Characteristics will be reported in listings.

